## **7 SAFETY ASSESSMENTS**

It is the responsibility of the PI to oversee the safety of the study. Research data will be reviewed in a timely manner; communication with the IRB will be documented in an open and timely manner in accordance with existing policies; source documentation will exist for all data fields/questions; explanations for deviations from the study protocol will be recorded; and all study files and documents will be maintained in organized files. The IRB will also determine whether currently or previously enrolled participants should receive notice of the unanticipated problem (and the potential for possible risk).

### **7.1 Data Safety Monitoring Plan**

This protocol presents minimal risks to the subjects and Unanticipated Problems Involving Risks to Subjects or Others, including adverse events, are not anticipated. In

the unlikely event that such events occur, Reportable Events [which are events that are serious or life-threatening and unanticipated (or anticipated but occurring with a greater frequency than expected) and possibly, probably, or definitely related] or Unanticipated Problems Involving Risks to Subjects or Others that may require a temporary or permanent interruption of study activities will be reported immediately (if possible), followed by a written report within 5 calendar days of the Principal Investigator becoming aware of the event to the IRB.

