### **The core components of interventions**

- For participants with abnormal biochemical markers, pharmacological therapy and diet modification are applied.
- Dietary education on phosphorus additives is applied specifically for retention of phosphorus or high serum phosphorus level.
- Exercise for bone and cardiovascular health.
- Osteoporosis medications are initiated according to the reimbursed criteria of National Health Insurance, otherwise medications are used with non-insurance payment.

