#### **Responsibilities**

1. Know or review patient's disease and care preferences.
2. Review, discuss, and update patient's health priorities on each visit.
3. Prescribe medications for chronic kidney disease and osteoporosis according to the results of blood and urine examination, and bone density.

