## **8 RISKS AND BENEFITS**

### **8.1 Risks**

The risk of participants in this study may have a minor risk in blood sampling. Except for a slight pain in the skin at the blood draw, the chance of bleeding from the puncture site or microbial infection at the puncture site is very small.0000

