### **9.2 Outcomes**

#### **9.2.1 Primary outcomes**

The primary outcome measures will be all-cause mortality, cardiovascular events, subsequent fracture rate, and fall rate from January 1, 2020 to December 31, 2020. The primary outcome measures will be collected during the baseline and follow-up (3-12 months) interviews in clinics.

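### The safety sections foresee only blood-draw risk, although the intervention is drugs, diet change and exercise; outcome events are not assessed as possible harms, and other treatment harms have no planned collection or summary

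*Combined protocol and SAP*

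**What the plan says.** - **Section 7.1** classes the study as low risk: "This protocol presents minimal risks to the subjects and Unanticipated Problems Involving Risks to Subjects or Others, including adverse events, are not anticipated". The next sentence treats any such event as improbable.
- **Section 7.1, reporting rule.** It covers "Reportable Events [which are events that are serious or life-threatening and unanticipated (or anticipated but occurring with a greater frequency than expected) and possibly"; the bracket then completes a requirement of at least a possible link to the study. The rule also covers unanticipated problems that could halt study activities. These go to the IRB at once if possible, and in writing no later than five calendar days after the principal investigator learns of them.
- **Section 8.1** says that participants "may have a minor risk in blood sampling", then describes pain, bleeding and infection at the puncture site. It names no other risk.
- **Section 5.1, core components:** "For participants with abnormal biochemical markers, pharmacological therapy and diet modification are applied". Exercise is a further component. Also, "Osteoporosis medications are initiated according to the reimbursed criteria of National Health Insurance", with payment outside the insurance where those criteria are not met.
- **Section 5.2** makes it a duty of the study physicians to "Prescribe medications for chronic kidney disease and osteoporosis according to the results of blood and urine examination, and bone density".
- **Section 9.2.1** names the primary outcomes as "all-cause mortality, cardiovascular events, subsequent fracture rate, and fall rate", collected at the baseline and follow-up interviews. Section 3 adds medical record review.
- **Section 6.1** schedules clinic visits, interviews, and blood and urine tests at months 3, 6, 9 and 12. No column is for adverse events.
- **Section 9.4** plans descriptive statistics for baseline data and the primary and secondary outcomes. It has no safety summary.

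**The concern.** The safety sections describe a study that does nothing to participants beyond taking blood. The intervention section describes one that starts drugs and exercise in older patients with reduced kidney function and high fracture risk. These accounts do not match, and the data collection follows the first.

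Two things are at stake. First, a fall or fracture that occurs during study exercise would be tallied as an outcome, with no record of its link to the exercise. Second, a drug or exercise harm that is neither one of the four outcomes nor visible in the laboratory panel would be recorded only if someone happened to raise it. Section 8.2 hopes to spread this model of care, and a pilot that informs such a step should be able to say what harms it saw.

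**Working it through.** **Where each kind of harm goes under the plan as written**

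| Kind of event | Collected? | Attributed to drug or exercise? | Summarised as safety data? |
|---|---|---|---|
| Death, cardiovascular event, fracture, fall | Yes (3, 9.2.1) | No | No; only as outcomes (9.4) |
| Biochemical change | Yes, repeat tests (6.1) | No | No; paired before-after test (9.4), which describes the average and not individual abnormal values |
| Serious, unanticipated, at least possibly related event | Reported to the IRB once known (7.1) | Yes, as a condition of reporting | No |
| Any other drug or exercise harm | No scheduled question (6.1) | No | No |

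**The frequency trigger.** An anticipated serious event becomes reportable only when it exceeds an expected frequency. The plan states no such frequency for any event, and the study has a single arm, so there is no concurrent rate to compare with.

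**Plausibility check on fractures.** The plan gives no expected number of adverse events, and section 9.1 sets the sample size by funding, so there is no planned figure to reproduce. Inputs: 60 participants (Study Summary), at most one year of follow-up (sections 3 and 9.2.1), and the background fracture rates in section 2.1. That section lists five rates for four stage groups, so the mapping to stage is unclear and all five are shown.

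Expected fractures m = person-years × rate / 1000. Poisson chance of at least one = 1 − exp(−m).

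| Rate per 1000 person-years | m in 60 person-years | Chance of at least one |
|---|---|---|
| 15.0 | 0.90 | 59% |
| 20.5 | 1.23 | 71% |
| 24.2 | 1.45 | 77% |
| 31.2 | 1.87 | 85% |
| 46.3 | 2.78 | 94% |

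Sixty person-years is the maximum, because enrolment and follow-up share one calendar year. If follow-up averaged half a year (an assumption), person-years = 60 × 0.5 = 30:

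- rate 15.0: m = 0.45, chance 36%
- rate 46.3: m = 1.39, chance 75%

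Cross-check from the entry thresholds for major osteoporotic fracture in section 4.1 (12.5% for women, 15% for men, over 10 years). With a constant hazard assumed, the yearly rate is −ln(1 − p)/10:

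- p = 0.125: 0.01335 a year; × 60 = 0.80; chance 55%
- p = 0.15: 0.01625 a year; × 60 = 0.98; chance 62%

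Deaths, cardiovascular events and falls would add to this, but the documents give no rates for them.

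**What systematic collection could show.** For a harm with true risk p, the chance of at least one case in 60 is 1 − (1 − p)^60: 45% at 1%, 70% at 2%, 95% at 5% and 99.8% at 10% (the risks are assumed). No case in 60 would give a one-sided 95% upper bound of 1 − 0.05^(1/60) = 4.9%. A pilot of this size can reveal common harms but cannot exclude uncommon ones.

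**The case against.** **The four outcomes are counted.** A reader might infer that harms would go uncounted altogether. The documents do not support that. Deaths, cardiovascular events, fractures and falls are collected at interview and from records and are described in the analysis. Repeat blood and urine tests would show some biochemical harm. This objection stands, and it confines the gap to attribution, safety classification and other harms.

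**A reporting route exists.** A reader might also infer that an exercise-related fracture has no way into safety review. If serious, at least possibly related and regarded as unanticipated, it goes to the IRB, and problems that could halt the study have their own limb. Since no event is listed as expected, one can argue that all serious related events count as unanticipated. Against that, events chosen as primary outcomes are easily called anticipated, and the frequency trigger then has nothing to work with. The plan leaves this open.

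**The sentence may deny only unanticipated problems.** That is a possible reading, but the sentence expressly takes in adverse events, and the plan has no list of anticipated ones to support the narrower meaning.

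**Background fractures are not research harms.** This stands. The fracture figures show that serious clinical events were plausible in this population. They do not show that the intervention would cause them, and they do not by themselves disprove the statement in 7.1.

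**Consent.** It is tempting to add that participants were given an inaccurate risk statement. The consent form is not among the documents reviewed, and section 8.1 is protocol text, so that cannot be concluded.

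**Conclusion.** The point holds in limited form and should be corrected. Sections 7.1 and 8.1 do not fit the intervention in sections 5.1 and 5.2. The four outcome events are counted but not assessed as possible effects of drug or exercise, and other treatment harms have no collection or analysis plan. The frequency trigger cannot be applied.

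The main finding rests on the text and needs no arithmetic. The fracture range (0.9 to 2.8 expected, 59% to 94% chance of at least one) is supporting context. It assumes a full year for all 60, a Poisson count and an unclear mapping of rates to stages; with half a year on average the chance is 36% to 75%. Section 12.1 reports that only 5 participants were enrolled and none completed. That is a result and does not change the assessment of the plan.

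**What to change.** 1. Reconcile sections 5.1, 7.1 and 8.1. Remove from 7.1 the statement that adverse events are not expected, and add the risks of the study drugs and of exercise to 8.1.
2. Add one adverse-event page to the existing visits at months 3, 6, 9 and 12, recording seriousness and relation to drug or exercise. Complete it for primary-outcome events too.
3. Add to 9.4 a descriptive safety summary: numbers of participants and events, by seriousness and relation.
4. State in 7.1 that serious primary-outcome events judged at least possibly related remain reportable. This must accompany any list of expected events: under the present rule, naming fractures or deaths as expected would make them reportable only above an expected frequency, and so could narrow reporting.
5. Either give a reference rate for the frequency trigger or remove the trigger. For fractures, the section 2.1 rates times person-time would serve once their mapping to stage is clarified.

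The cost is revised wording, which needs committee approval under section 11.1, one form page and some coordinator time. No extra visits or tests are needed.

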## **8 RISKS AND BENEFITS**

### **8.1 Risks**

The risk of participants in this study may have a minor risk in blood sampling. Except for a slight pain in the skin at the blood draw, the chance of bleeding from the puncture site or microbial infection at the puncture site is very small.0000

### **8.2 Benefits**

The potential benefit of the evaluation of this integrated approach will be to disseminate optimal care of CKD-MBD and osteoporosis. We expect that this approach will result in better care for the participants with CKD.

## **STATISTICAL CONSIDERATIONS**

### **9.1 Sample Size**

As this is a pilot study, we did not complete a formal sample size calculation. The chosen sample size is based upon the estimated number of patients that the funding supports their blood and urine examination, and bone density examination.

### **9.2 Outcomes**

#### **9.2.1 Primary outcomes**

The primary outcome measures will be all-cause mortality, cardiovascular events, subsequent fracture rate, and fall rate from January 1, 2020 to December 31, 2020. The primary outcome measures will be collected during the baseline and follow-up (3-12 months) interviews in clinics.

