**STUDY SUMMARY**

|                                       |   |
|---------------------------------------|---|
| Title                                 | The effect of multi-faceted intervention on osteoporosis and CKD-MBD  |
| Methodology                           | Prospective interventional cohort study   |
| Study Duration                        | Estimated duration for the main protocol is from January 1, 2020 to December 31, 2020.  |
| Study Center(s)                       | Multi-center (National Taiwan University Hospital and National Taiwan University Hospital Chu-Tung Branch)  |
| Objectives                            | To evaluate the effect of pharmacological therapy and behavioral interventions among patients with chronic kidney disease having risk of osteoporosis related fracture  |
| Number of Subjects                    | 60 subjects in a single arm   |
| Diagnosis and Main Inclusion Criteria | 
Inclusion criteria
 
 
1. Age > 50 years
 
2. CKD stage 3-4, and eGFR >20 mL/min/1.73m^2
 
3. FRAX® screening threshold: risk of hip fracture (HF) and major osteoporotic fracture (MOF) (HF: men> 6%, women > 7%; MOF: men> 15%, women> 12.5%)
 
 
Exclusion criteria
 
 
1. Unable to consent (e.g. dementia)
 
2. Have cancer under treatment
 
3. Have acute coronary syndrome (unstable angina, non-ST elevation myocardial infarction, ST-elevation myocardial infarction) or stroke in 3 months.
 
4. Limited cognitive or physical function for execute the intervention
 
 |
| Interventions                         | 
 
1. Pharmacological therapy for chronic kidney disease-mineral bone disorder and osteoporosis
 
2. Behavioral interventions including diet modification and exercise for bone and cardiovascular health
 
   |
| Statistical Methodology               | 
Primary outcome: all-cause mortality, cardiovascular events, subsequent fracture rate, and fall rate
 
Secondary outcome: biochemistry laboratory tests before and after multifaceted interventions
   |

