### **3 STUDY DESIGN**

The design is a pilot study with data collection through interviews, and medical records. There is one study arm: the intervention. A description of multi-faceted intervention on osteoporosis and CKD-MBD can be found in STUDY INTERVENTIONS. The pilot will take place at two primary clinical care practices in National Taiwan University Hospital and its Chu-Tung Branch in Taiwan. 60 patients will be enrolled and followed for up from January 1, 2020 to December 31, 2020 with interviews and medical record reviews. Participants will undergo a baseline and follow-up interview to collect patient reported baseline and outcome measures.

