## **6 STUDY PROCEDURES**

### **6.1 Schedule of Evaluation for Patient Population**

| Time period          | Screening | Informed Consent (Enrollment) | Clinic visit | Interviews (Patient Reported Outcomes) | Blood and Urine Examination | Bone density and Thoracolumbar x-ray film |
|----------------------|-----------|-------------------------------|--------------|--|-----------------------------|---|
| Enrollment (Day 1)   | x         | x                             | x            |  | x                           | x   |
| Follow-up Evaluation |           |                               | x            | x                                      | x                           |   |

|                                |  |  |  |  |  |  |
|--------------------------------|--|--|--|--|--|--|
| (3,6,9,12 th month) |  |  |  |  |  |  |
|--------------------------------|--|--|--|--|--|--|

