### **9.4 Data Analyses**

We will calculate descriptive statistics for participants' baseline characteristics and primary and secondary outcomes. The bivariate analysis will be performed using the t-test or Mann-Whitney U test for continuous variables with normal or non-

normal distribution, respectively. Chi-squared test for categorical variables will be used to test correlations between baseline characteristics, change of laboratory results and outcomes. The paired t-test will be used to examine the difference between before and after the interventions. Stepwise multivariate logistic regression models will be used to identify the correlates of outcomes after adjusting for potential confounders. All tests conducted will be two-tailed, and significance will be set at  $p < 0.05$ .

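### Enrolment, follow-up and the primary outcome window share calendar year 2020, so month 12 is essentially out of reach, follow-up is unequal, and the planned analyses specify no time at risk

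*Combined protocol and SAP*

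**What the plan says.** Three places use the same calendar year for three different purposes.

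- Study Summary, for the study as a whole: "Estimated duration for the main protocol is from January 1, 2020 to December 31, 2020".
- Section 3, for enrolment and follow-up together: "60 patients will be enrolled and followed for up from January 1, 2020 to December 31, 2020 with interviews and medical record reviews".
- Section 9.2.1, for the primary outcomes: "all-cause mortality, cardiovascular events, subsequent fracture rate, and fall rate from January 1, 2020 to December 31, 2020".

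The visit schedule in Section 6.1 runs on a different clock. It starts at "Enrollment (Day 1") and places follow-up evaluations at "3,6,9,12 th month". It gives neither a last enrolment date nor a tolerance around visits.

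On ascertainment, Section 9.2.1 says "The primary outcome measures will be collected during the baseline and follow-up (3-12 months) interviews in clinics", and Section 3 describes "data collection through interviews, and medical records".

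On analysis, Section 9.4 opens with descriptive statistics for the outcomes and continues: "Chi-squared test for categorical variables will be used to test correlations between baseline characteristics, change of laboratory results and outcomes". It then adds stepwise logistic regression for correlates of the outcomes. It mentions no person-time, offset, censoring rule or fixed risk horizon.

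**The concern.** A participant's follow-up ends at the earlier of month 12 and 31 December 2020. For anyone who enters after the first days of January, the calendar date comes first. The month-12 visit then cannot take place within the stated dates, and each later entrant is observed for less time.

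Three things follow for the primary outcomes.

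- The proportion with an event mixes people observed for different lengths of time. It estimates no defined risk, and it would change with the accrual pattern even if the underlying event rates did not.
- Fractures and falls are called rates, but nothing says what they are divided by.
- The outcome window opens on 1 January for everyone. Read literally, a fall in February counts for a participant who enrolled in May, before any intervention.

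This is a single-arm pilot without a power calculation, so the descriptive event figures are its main product. Those are the figures affected.

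**Working it through.** The plan gives no event rate, person-time or power to reproduce; Section 9.1 says that no formal calculation was made. The check is calendar arithmetic.

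**Inputs from the documents.** N = 60 and closure on 31 December 2020 (Section 3); visits at months 3, 6, 9 and 12 from Day 1 (Section 6.1).

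**Assumptions.** Entry is uniform over the first A months of 2020, with A = 12, 6 or 3, and there are no deaths or dropouts. The documents give no accrual pattern, hence the range.

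**Step 1: who can reach month 12.** There are 365 days from 1 January to 31 December 2020. If 12 months means 365 days after entry, only entry on 1 January qualifies. If it means Day 365 with enrolment as Day 1, entry on 2 January also qualifies. Either way only the first days of January do.

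**Step 2: follow-up.** For entry at month e, follow-up is 12 − e months. Mean follow-up is 12 − A/2, person-years (PY) are 60 × mean/12, and the number reaching month m is 60 × min(1, (12 − m)/A).

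| Accrual A | Mean follow-up | PY | Reaching months 3 / 6 / 9 / 12 |
|---|---|---|---|
| 12 months | 6.0 months | 30 | 45 / 30 / 15 / about 0 |
| 6 months | 9.0 months | 45 | 60 / 60 / 30 / about 0 |
| 3 months | 10.5 months | 52.5 | 60 / 60 / 60 / about 0 |
| Full 12 months each | 12 months | 60 | 60 / 60 / 60 / 60 |

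**Step 3: precision with zero events.** The upper end of the two-sided exact 95% Poisson interval is chi-squared(0.975, 2 df)/2 = 3.689 events. Per PY this is:

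- 3.689/30 = 0.123
- 3.689/45 = 0.082
- 3.689/52.5 = 0.070
- 3.689/60 = 0.061

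That is 12.3, 8.2 and 7.0 per 100 PY, against 6.1.

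**Step 4: the right clock for falls.** If falls are known only from interviews, the time actually covered ends at the last reachable interview, which is follow-up rounded down to a multiple of 3 months.

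- A = 12: 15 × (9 + 6 + 3 + 0)/12 = 22.5 PY
- A = 6: 30 × (9 + 6)/12 = 37.5 PY
- A = 3: 60 × 9/12 = 45 PY

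Dividing interview-reported falls by time to 31 December would understate the fall rate by 1 − 22.5/30 = 25%, 1 − 37.5/45 = 17% or 1 − 45/52.5 = 14%, unless medical records capture the later falls.

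**Step 5: can fractures be modelled?** Section 2.1 lists five incidence rates for four stage groups, so only the full listed range is used, as an illustration: 15.0 to 46.3 per 1000 PY. Expected fractures are 60 × 0.015 = 0.9 to 60 × 0.0463 = 2.8 in 60 PY, and 30 × 0.015 = 0.45 to 30 × 0.0463 = 1.4 in 30 PY. That is too few for a regression model in either case.

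**The case against.** **The dates may be soft.** The Study Summary calls the duration estimated, and the 3-12 months in Section 9.2.1 could mean variable follow-up to a common closing date. But Sections 3 and 9.2.1 repeat the dates without qualification, and Section 9.2.1 makes them part of the outcome definition. If variable follow-up was intended, time at risk needs more attention, not less.

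**A visit tolerance would help.** This is true. With an assumed one-month window, month 12 needs 11 months of follow-up. Under 3-month accrual, 60 × 1/3 = 20 participants would then qualify. No window is stated, and follow-up would still be unequal.

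**Descriptive statistics could be per person-year.** They could, but Section 9.4 does not say so, and the chi-squared and logistic analyses would still ignore time.

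**It is a pilot, and events will be few.** This stands against insisting on a model: for fractures, rates alone are the realistic output. It does not excuse a schedule that cannot be completed or a rate without a denominator.

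**A simple person-time remedy has its own faults.** This also stands. Running everyone's clock to 31 December would understate falls collected at interview, as step 4 shows. Plain Poisson intervals on total falls would be too narrow if some people fall repeatedly. The fix allows for both.

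**Two stronger readings are not supported.** A reader might contrast long and short follow-up, find a large odds ratio at a constant event rate, and call it bias. No planned analysis compares participants by length of follow-up, and there is one arm, so follow-up cannot differ between arms. Associations with baseline factors or laboratory changes are biased only if those factors are related to enrolment date, and nothing in the documents shows that. A reader might also take the results in Section 12 (5 enrolled, none completing) as proof. They are consistent with the point, but they are results. Section 12 attributes termination to one-year funding and gives no entry dates for the five.

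**Conclusion.** The point holds and should be fixed. On the stated dates, month 12 is essentially unreachable under any staggered enrolment, follow-up length depends on entry date, the outcome window is not tied to Day 1, and the planned analyses specify no time at risk. The observed event proportion is not a 12-month risk and depends on accrual.

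Under uniform accrual without deaths or dropout, the shortfall from 60 person-years is 30, 15 or 7.5 for accrual over 12, 6 or 3 months. The pattern is assumed; the conflict between the dates and the schedule is not. The conclusion extends to undefined and accrual-dependent event figures. It does not extend to demonstrated bias in the correlates.

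**What to change.** **Section 9.2.1.** Count events and person-time from each participant's Day 1, and exclude events before it.

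- Deaths, cardiovascular events and fractures, which record review can also capture: end person-time at the earliest of death, withdrawal or loss to follow-up, month 12, or 31 December 2020. Where first events are counted, also end it at the first event.
- Falls collected at interview: end person-time at the last completed interview.
- Report events per person-year, with exact Poisson intervals for deaths and first events. For total falls, use an interval that allows for repeat falls within a person (for example negative binomial or robust variance), or report first falls only.

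**Section 9.4.** Replace logistic regression for these outcomes by a model with a log person-time offset only where event counts support one. Otherwise report rates alone.

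**Sections 3, 6.1 and 9.2.1.** Reconcile them by stating the follow-up achievable by 31 December 2020, or by setting separate enrolment and follow-up periods. A full 12 months for everyone needs about 12 + A months in total, or 24 months if accrual takes 12.

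**Cost.** Event and interview dates must be recorded, and withdrawal dates where they end follow-up. The stated follow-up becomes shorter than 12 months unless the study period is extended.
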